Title: Comparison of fentanyl- bupivacaine and clonidine- bupivacaine for breakthrough pain in advanced labor in patients with continuous epidural analgesia

Columbia University Medical Center
Attached to Protocol: IRB-AAAL4101
Principal Investigator: [name]
Participation Duration: 1 day
Anticipated Number of Subjects: 250

PROTOCOL

Study Purpose and Rationale:

Epidural analgesia is a popular choice among patients for relief of severe pain associated with labor and delivery. Currently, at our institution we use a continuous infusion of low dose local anesthetic and narcotic (12 ml/hr of 0.0625% bupivacaine with 2 micrograms/ml fentanyl) after the initial spinal or epidural dose to maintain patient comfort until delivery. This dose of the infusion is chosen because it often provides adequate comfort without interfering with the mobility of the patient and her ability to effectively push during delivery. However, this low-dose epidural infusion strategy often results in recurrence of pain after an initial pain-free period. This recurring pain is known as breakthrough pain and is alleviated by administering small boluses of analgesics via the epidural catheter.

The pain occurring in labor is initially of visceral origin and is mediated by pain fibers originating from the low thoracic and upper lumbar segments of the spinal cord. As labor progresses to the late first phase (also known as transitional stage), pain sensations originating from the distension of the pelvic floor, vagina and perineum adds a somatic component to labor pain. This type of breakthrough pain, mediated by nerve fibers originating from the sacral nerves at dermatomes S2-S4, is often difficult to treat. Patients may experience inadequate analgesia even after boluses of analgesics are administered. Inadequate analgesia is deleterious due to subjective discomfort with its associated neurohumoral and physiological changes, and can be an initiator of the urge to bear down (push). Pushing before complete dilation of the cervix may lead to swelling, cervical injury and premature exhaustion of the mother. Adequate pain control will allow the cervix to fully dilate and motivate the mother to push effectively at the appropriate time. Although requests from patients to alleviate late stage breakthrough pain are common, there are no established data in the literature regarding the most effective strategy for pain management in this stage of labor.

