This study is designed to compare the efficacy of two treatments for controlling late first stage breakthrough pain during labor: clonidine-bupivacaine versus fentanyl-bupivacaine. Both strategies are used at Columbia University Medical Center (CUMC) in this clinical situation, and there is no clear evidence whether one is superior.

Study Design and Procedures:

After obtaining consent, the patients will be randomized into two groups using a random allocation table. At the onset of late stage breakthrough pain with a Visual Analogue Scale (VAS) greater than or equal to 5/10, subjects will randomly receive either a mixture of 100 mcg

of clonidine and 12.5 mg of bupivacaine for a total volume of 10 ml ("CLON" group) and the other group will receive 100 mcg of fentanyl and 12.5 mg of bupivacaine for a total volume of 10 ml ("FENT" group). Group assignment will be performed by opening a previously prepared numbered opaque envelope containing the assignment "CLO" or "FENT".

The patient will be evaluated every 5 minutes for 15 minutes. If the patient reports a decrease in the VAS pain score by 4 points or more, the treatment will be declared a success. If the patient does not report a decrease in VAS score by 4 or more, the treatment will be declared a failure. If the treatment fails within 25 minutes from the end of injection of the initial study drug, the patient will receive the alternative of the initial treatment, which is 100 mcg of fentanyl or 100 mcg of clonidine (i.e., whichever drug was NOT given in the study mixture) with bupivacaine 12.5mg, diluted to a total of 10ml with sterile saline, via the epidural catheter (the observer will remain blinded to the identity of the medication). If this intervention fails to alleviate the pain, the caretakers will administer 5ml of 2% lidocaine via the epidural catheter. If the pain score still has not fallen by 4 or more points from baseline, 15 min after the dose of lidocaine the epidural catheter will be considered to be non-functioning.

All drug handling/distribution/administration will be conducted in accordance with the policies of the Research Pharmacy and Columbia University Medical Center.

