Demographic and labor data (patient age, height, and weight, parity, hours in labor, cervical dilation and fetal station), details of labor analgesia preceding administration of the study drug (duration, type and amount of epidural or spinal analgesics, or other forms of analgesia), maternal and fetal heart rate and maternal blood pressure prior to and following administration of the study drug will be collected along with other clinical variables.

The study terminates upon delivery of the baby. Maternal and fetal hemodynamic data (maternal BP and pulse, fetal heart rate) and other clinical data will be obtained for 2 hours after the study dose, or until delivery, whichever is earlier. Neonatal Apgar scores as well as the mode of delivery will be collected.

Patients will be recruited by a study investigator after the establishment of labor epidural analgesia. The participants will be patients of the study team physicians. Informed consent with written documentation will be obtained from the research participant.

STATISITCAL PROCEDURES

The primary outcome is "success" or "failure" of the treatment as defined above. A clinically significant difference between the two treatments would be a 0.3 (30%) difference in probabilities for adequate analgesia. Assuming that the inferior treatment is successful in half of all patients, we aim to determine if the superior treatment is successful in 80%. For a power of 80% and an alpha of 0.05, this requires 45 subjects per group, so we plan on studying 100 overall.

To obtain 100 subjects who require a dose for breakthrough pain in the late first stage or second stage of labor, we may need to recruit and consent more than 250 subjects, since women will be

recruited after they are comfortable with their epidural analgesia, and it will not be known if they will eventually need a supplemental dose. Continuous data (VAS, total use of analgesics, maternal and fetal heart rate, maternal blood pressure) will be analyzed using ANOVA (with repeated measurements as appropriate) and categorical data (use of ephedrine, supplemental oxygen, fluid boluses and positional changes associated with administration of analgesics, instrumental delivery, cesarean section) will be analyzed using Chi-Squared analysis with Yates' continuity correction or Fisher's exact test as appropriate.

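### Total analgesic use, tested by ANOVA, cannot be read as a measure of lasting pain relief because it includes assigned and rule-driven doses and possibly the background infusion

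*Combined protocol and SAP*

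**What the plan says.** The primary outcome is binary and short-term. Under Study Design and Procedures: "If the patient reports a decrease in the VAS pain score by 4 points or more, the treatment will be declared a success". The scheduled pain readings are brief: "The patient will be evaluated every 5 minutes for 15 minutes". The only later score described comes 15 minutes after lidocaine, in women whose pain has persisted after both mixtures.

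A woman whose first mixture fails receives the other mixture: 100 mcg of the drug she was not assigned, again with 12.5 mg of bupivacaine. If that fails she receives lidocaine. In the background is the institution's epidural infusion, described under Study Purpose and Rationale as "12 ml/hr of 0.0625% bupivacaine with 2 micrograms/ml fentanyl" and as maintaining comfort until delivery.

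On analysis, the Statistical Procedures section says: "Continuous data (VAS, total use of analgesics, maternal and fetal heart rate, maternal blood pressure) will be analyzed using ANOVA", with repeated measurements as appropriate. It does not say which analgesics enter the total, in what unit, from when or until when. On follow-up, the protocol says "The study terminates upon delivery of the baby", and that hemodynamic and other clinical data are collected for 2 hours after the study dose or until delivery if that is earlier. It does not say whether analgesic use is among those data. No duration of relief, time to next request or top-up count is defined.

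**The concern.** The rationale describes pain that returns after an initial pain-free period and gives a reason to want relief that lasts: "Adequate pain control will allow the cervix to fully dilate and motivate the mother to push effectively at the appropriate time". A reader will therefore look for evidence on what happens after the first quarter of an hour, and total analgesic use is the natural place to look. Three parts of that total are not a response to how long the mixture lasted:

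- **The assigned dose.** FENT always contributes 100 mcg of fentanyl; CLON contributes it only after failure.
- **The second dose required after failure.** It is triggered by the primary outcome, so it carries the same information again.
- **The infusion, if counted.** It accumulates with time whichever mixture was given.

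At stake is a secondary result. A fentanyl difference created by the design could be reported as opioid sparing. A mixture that works early but wears off sooner could go unrecognised. Because the variable is undefined, the choice of what to count could also be made after the data are seen.

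**Working it through.** **1. The plan's own figure.** Inputs from Statistical Procedures: success 0.50 v 0.80, alpha 0.05, power 0.80. Two-sided, pooled: n = [1.96 × √(2 × 0.65 × 0.35) + 0.842 × √(0.25 + 0.16)]² / 0.30² = 38.5. The continuity correction multiplies by ¼ × [1 + √(1 + 4/(38.5 × 0.30))]² and gives 44.9, so 45 per group, as stated. At 50 per arm, exact power is about 0.85 by Fisher's test or Yates' chi-squared. Nothing below changes this.

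**2. Fentanyl by construction.** Let p be the success rate in CLON. Mean fentanyl from study and second doses is 100 mcg in FENT and 100 × (1 − p) in CLON, so the difference is 100 × p.

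| Success, same in both arms | FENT mean | CLON mean | Difference |
|---|---|---|---|
| 50% | 100 mcg | 50 mcg | 50 mcg |
| 65% | 100 mcg | 35 mcg | 65 mcg |

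Simulation at 65% success, with equal durability and infusion fentanyl included, also gave about 65 mcg. Power to declare that difference significant was near 100% at 50 per arm.

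**3. The second dose.** At 50% v 80% success, its mean bupivacaine differs by (0.50 − 0.20) × 12.5 = 3.75 mg, even if the mixtures last equally long.

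**4. The infusion.** 0.0625% is 0.625 mg/ml. At 12 ml/h this is 7.5 mg of bupivacaine per hour, and 12 × 2 = 24 mcg of fentanyl per hour. One 12.5 mg bolus equals 12.5 / 7.5 = 1 h 40 min of infusion.

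To show the dilution, take the 3.75 mg difference as the signal. The bolus SD is 12.5 × √((0.25 + 0.16)/2) = 5.66 mg, and the total SD is √(5.66² + (7.5 × s)²), where s is the SD in hours of infusion time after the dose. The documents do not give s, so a range is shown (two-sided t test, 50 per arm):

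| s (h), assumed | Total SD (mg) | Power |
|---|---|---|
| 0 (boluses only) | 5.66 | 0.91 |
| 0.25 | 5.96 | 0.88 |
| 0.5 | 6.79 | 0.78 |
| 0.7 | 7.72 | 0.67 |
| 1.0 | 9.40 | 0.51 |
| 1.5 | 12.59 | 0.31 |

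If totals stop at 2 hours, time lies between 0 and 2 h, so s cannot exceed 1 h; the last row applies only to follow-up to delivery. The signal here is the gap in initial success, so the table shows dilution by infusion time and says nothing about durability.

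**5. Durability itself.** This was simulated with follow-up to delivery and 50 per arm. Assumptions: gamma time to delivery with mean 1.5 to 4 h and SD half the mean; 65% initial success in both arms; later top-ups of 12.5 mg at 0.2 or 0.4 per hour, halved in the more durable arm.

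| What is compared | Power to detect the halved top-up rate |
|---|---|
| Total bupivacaine with infusion | 13%–46% |
| Further boluses, including the second dose | 19%–84% |
| Later top-ups only | 33%–89% |

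Time to delivery explained 41%–71% of within-arm variance when infusion was counted, and 4%–26% when only further boluses were counted.

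**The case against.** The strongest reply is that an undefined variable has been read in its worst form. Several parts of that reply stand.

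- **What is counted.** The plan does not say that the infusion enters the total. A reader might infer that the total mainly measures time to delivery. That holds under the simulation's assumptions only if infusion is included; with boluses alone, time explains a minor share.
- **The window.** The only stated collection window is 2 hours or delivery. If it covers analgesic use, infusion can add at most 2 × 7.5 = 15 mg, and the loss of power is smaller.
- **Noise or bias.** A reader might infer that labor length can mimic a treatment effect. Randomisation balances time to delivery in expectation. It is noise unless a drug changes labor length, which the documents do not suggest.
- **The aim.** A reader might infer that the trial fails an objective of showing control until delivery. The stated aim is efficacy for late first stage breakthrough pain; lasting control appears in the rationale and is not an endpoint.
- **Other readings.** The ANOVA sentence sets no end time for VAS, and there is a score after lidocaine, though only in a selected group. Further top-ups would also raise the total. It is therefore too strong to say that the trial cannot show a difference in durability.

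The reply does not answer the fentanyl artefact or the second-dose overlap. Neither depends on labor length, and randomisation removes neither. Leaving the content of the total open is also a defect in a variable that will be tested.

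**Conclusion.** The point holds as a weakness in a secondary efficacy variable. As written, total analgesic use cannot be interpreted as duration of pain control.

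The firmest part needs no outside assumption: any fentanyl total that includes the study dose differs by 100 mcg times the CLON success rate before later top-ups are considered, which is 50 mcg at 50% success in both arms. The second-dose contribution, 3.75 mg of bupivacaine, follows from the plan's own success rates and restates the primary outcome. The infusion contribution is conditional on its being counted, and its size depends on the window and on an assumed spread of times. The durability power ranges are illustrative, because the documents give neither top-up rates nor times to delivery.

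The documents do not support the stronger conclusion that the trial's main comparison is undermined. The binary primary outcome and the 45 per group do not use this variable. The change should be made, but the trial does not stand or fall on it.

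**What to change.** 1. Do not test total analgesic use as an efficacy outcome. Report totals by drug and by arm as a description of exposure.
2. Compare the arms, as randomised, on the number of further epidural boluses after the study dose, excluding the infusion and the assigned dose. Use a fixed window, for example the 2 hours already stated or delivery if earlier. Fit a count model with log time at risk as an offset; ratios of boluses per hour for each woman are unstable when delivery comes quickly.
3. Show protocol rescue boluses and later top-ups separately, because rescue repeats the primary outcome.
4. Add a supportive Kaplan-Meier curve of time to first further bolus, with delivery as a censoring or competing event. It should not lead: with rescue counted as an event, a log-rank test largely repeats the primary outcome. In one simulated setting with assumed top-up rates, its power for a halved top-up rate was 0.39, against 0.42 for the total with infusion and 0.76 for the bolus-only comparison.
5. State that results after a failure reflect initial assignment plus crossover to the other drug.
6. Reconcile the 15-minute evaluation period with the 25-minute limit in the failure rule, since together they decide which boluses count as protocol rescue.

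The cost is analysis-plan wording and abstraction of bolus and delivery times from the record, with no added patients or visits. Some women will have short follow-up because of early delivery. A 2-hour window also captures fewer top-ups than the follow-up to delivery used in the simulations, so power for later top-ups may be lower than those figures.

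### The VAS comparison, a non-primary analysis, does not use the pre-dose score as a covariate and does not say which readings or which contrast give the result

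*Combined protocol and SAP*

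**What the plan says.** All references are to the combined protocol and SAP.

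- **Planned VAS analysis (Statistical Procedures).** "Continuous data (VAS, total use of analgesics, maternal and fetal heart rate, maternal blood pressure) will be analyzed using ANOVA". A parenthesis then allows repeated measurements where appropriate. The sentence covers VAS, analgesic use, heart rates and blood pressure together. It names no baseline covariate, no time points and no tested effect.
- **Readings (Study Design and Procedures).** Treatment is given "At the onset of late stage breakthrough pain with a Visual Analogue Scale (VAS) greater than or equal to 5/10", so a pre-dose score must be recorded. After the dose, "The patient will be evaluated every 5 minutes for 15 minutes", which implies readings at 5, 10 and 15 minutes.
- **Primary outcome.** "The primary outcome is 'success' or 'failure' of the treatment as defined above". The definition is a change from the pre-dose score: "If the patient reports a decrease in the VAS pain score by 4 points or more, the treatment will be declared a success".
- **Sample size.** It rests on the binary outcome alone, at 50% versus 80% success: "For a power of 80% and an alpha of 0.05, this requires 45 subjects per group, so we plan on studying 100 overall".
- **Crossover.** After failure within 25 minutes of the end of injection, the woman receives the other study mixture. Nothing in Statistical Procedures says whether VAS readings taken after that dose enter the VAS analysis.

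**The concern.** A four-reading repeated-measures ANOVA (0, 5, 10 and 15 minutes) can be read in two ways, and neither uses the pre-dose score well. The group main effect averages in a reading taken before any study drug was given. The group-by-time interaction spreads the contrast over 3 degrees of freedom. Dropping the pre-dose score avoids both problems but discards what it tells us about later pain.

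The sentence also leaves open which of these is the VAS result. They answer different questions and can disagree, so the choice could be made after the data are seen. At stake are the precision and interpretability of a secondary comparison. It would carry more weight if the true difference in success were well below 30 percentage points.

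**Working it through.** **1. The plan's own figure.** Inputs: 0.50 and 0.80, mean 0.65, difference 0.30, power 80%, alpha 0.05 (taken as two-sided).

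- Uncorrected: n = [1.960·√(2·0.65·0.35) + 0.842·√(0.25 + 0.16)]² / 0.30² = (1.322 + 0.539)² / 0.09 = 38.5, so 39.
- With continuity correction: (38.5/4)·[1 + √(1 + 4/(38.5·0.30))]² = 44.9, so **45 per group**, as stated. Exact power of the Yates-corrected test is 0.807 at 45 and 0.853 at 50 per arm.

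Nothing in this calculation depends on how VAS is analysed.

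**2. Dilution.** If the arm difference is d at 5, 10 and 15 minutes and zero before the dose, the main effect over four readings is (0 + d + d + d)/4 = 0.75d, a 25% loss. Over the three post-dose readings it is d.

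**3. Power in closed form.** All VAS inputs here are assumptions: 50 per arm, d = 0.5 SD of one reading, equal correlation ρ between all readings. The noncentrality is effect/√(2·variance/50). At ρ = 0.5:

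| Analysis | Effect | Variance of the mean | Noncentrality | Power |
|---|---|---|---|---|
| Main effect, 0-15 min | 0.375 | (1+3ρ)/4 = 0.625 | 2.37 | 0.65 |
| Post-dose readings only | 0.5 | (1+2ρ)/3 = 0.667 | 3.06 | 0.86 |
| Post-dose mean, baseline-adjusted | 0.5 | 0.667 − ρ² = 0.417 | 3.87 | 0.97 |

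The group-by-time interaction has power 0.72 (noncentral F, 3 df). The gap can be small. With baseline correlation 0.1-0.2 and correlation 0.6 between post-dose readings, post-dose-only ANOVA has 0.82 and the adjusted analysis 0.83-0.84.

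**4. Simulation with the entry cut.** Assumptions: 50 per arm, baseline about 7.3 restricted to 5-10, follow-up SD 2.5, 1-point effect present from 5 minutes, serial correlation 0.6-0.7. The same readings (the post-dose mean) are compared without and with the covariate:

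| Baseline correlation | Unadjusted | Adjusted |
|---|---|---|
| 0.2 | 0.61-0.64 | 0.61-0.65 |
| 0.3 | 0.61-0.66 | 0.64-0.69 |
| 0.5 | 0.66-0.69 | 0.76-0.80 |

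Across both contrasts (the mean and the 15-minute score) the gain is about 0-2, 2-4 and 6-11 points respectively.

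**5. Which contrast.** Take 1 point as 1/2.5 = 0.4 SD, baseline correlation 0.3 and serial correlation 0.6. The adjusted variance is 0.733 − 0.09 = 0.643 for the mean and 1 − 0.09 = 0.91 for the 15-minute score.

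- Effect present from 5 minutes: mean 0.4/√(2·0.643/50) = 2.49, power 0.69; 15 minutes 0.4/√(2·0.91/50) = 2.10, power 0.55.
- Effect building linearly (one third, two thirds, all): the average effect is 0.267, so the mean has noncentrality 1.66 and power 0.38; 15 minutes is again 0.55.

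This closed form ignores the entry cut and the ends of the scale, so its values differ slightly from the simulated ones. The ordering shows the trade-off.

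**The case against.** The strongest reply is that the plan does not commit to an inefficient model. Repeated measures is conditional in the text, and nothing makes the pre-dose score a level of time. That stands: the plan is under-specified. A reader might infer that the stated method loses much of the arm contrast. That follows only if the pre-dose score is a time level and the main effect is tested (the 25%), or if the interaction is the test.

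A reader might also infer clearly more power from a large simulated gap. When the effect builds over 15 minutes, the 0-15 minute main effect has 0.26-0.27 and the adjusted 15-minute contrast 0.51-0.61. But the unadjusted 15-minute test already has 0.49-0.55, so most of that gap comes from changing the time point. If instead the effect is present from 5 minutes, the adjusted 15-minute contrast has 0.53-0.62 against 0.56-0.59 for the main effect, which is no clear improvement. Fixing on 15 minutes therefore has a cost.

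Finally, the consequence is limited. VAS has no stated hypothesis or rank, and the primary outcome already uses the change from pre-dose. The planned 50% versus 80% corresponds to 0.84 SD of change under normality. At ρ = 0.5 the main effect, post-dose-only ANOVA and interaction then all have power of about 0.98 or more. At ρ = 0.7 the main effect falls to 0.79, with 0.95 for post-dose only and 0.995 for the interaction.

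What the reply does not answer is that the score is collected and unused. On the same readings, adjustment was at least as powerful in every setting tried.

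**Conclusion.** The point holds as a modest refinement of a non-primary analysis. The plan names no baseline adjustment for VAS and leaves open the readings and the tested effect. The 25% dilution applies only to the group main effect with the pre-dose score as a time level and a constant post-dose effect. A post-dose-only analysis loses precision alone.

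The size of the gain cannot be fixed from the documents. The 0-2, 2-4 and 6-11 points quoted rest on an assumed 1-point effect, follow-up SD 2.5 and serial correlation 0.6-0.7. The low end is plausible because entry at 5/10 or more narrows the baseline range. The documents do not support reading this as a threat to the trial's main conclusion or its size: the success/failure test and the 45 per group stand.

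**What to change.** In Statistical Procedures, take VAS out of the general ANOVA sentence and state:

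- the 5-, 10- and 15-minute VAS scores taken before any crossover dose are analysed in a repeated-measures model with pre-dose VAS as a covariate (not a time level) and arm, time and arm-by-time terms;
- one adjusted contrast, chosen before data are seen, is the VAS result and is reported with a 95% CI: the 5-15 minute mean or the 15-minute difference.

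The choice is a trade-off: the 15-minute difference does better if the effect builds, the mean if it is present from 5 minutes. The sponsor should decide on the expected onset and on which quantity matters to users, and report the other as supportive.

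The cost is one or two sentences and slightly more analysis work, with no new data or patients. Whichever contrast is named, some power is given up if the effect takes the other shape.

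### Maternal blood pressure and maternal and fetal heart rates are compared only as group means, so brief or uncounted haemodynamic falls can be missed; a per-woman event comparison should be added

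*Combined protocol and SAP*

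**What the plan says.** The Study Design and Procedures section collects blood pressure and heart rates before the study dose and after it. The post-dose data "will be obtained for 2 hours after the study dose, or until delivery, whichever is earlier". No measurement interval is stated.

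The Statistical Procedures section then gives two analyses:

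- **Continuous data.** These include "maternal and fetal heart rate, maternal blood pressure) will be analyzed using ANOVA (with repeated measurements as appropriate").
- **Categorical data.** The list is ephedrine use, oxygen, fluid boluses and "positional changes associated with administration of analgesics, instrumental delivery, cesarean section", compared by "Chi-Squared analysis with Yates' continuity correction or Fisher's exact test as appropriate".

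On the newborn and delivery, "Neonatal Apgar scores as well as the mode of delivery will be collected".

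The plan gives no threshold for hypotension, maternal bradycardia or a fetal heart rate abnormality. It has no lowest-value or worst-change summary and no proportion of women affected. It sets no time window or other rule for when a treatment counts as associated with the analgesic.

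**The concern.** Haemodynamic harm from a single epidural bolus is a question of which women had an episode. A comparison of means answers a different question. A deep but short fall in a minority of women moves the arm mean very little, and a fall that has been treated is followed by readings nearer normal. A short fall in fetal heart rate is diluted in the same way.

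The treatment comparisons pick up some of this, but they depend on an episode being treated and then counted under an undefined association. They also do not separate maternal from fetal reasons for oxygen or repositioning.

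The protocol says both mixtures are already used at the institution and that neither is clearly superior. A difference in brief hypotension or fetal heart rate falls would bear on the choice between them, and the planned analysis could fail to show it.

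**Working it through.** **Plan's own figure.** The only sample-size figure concerns the primary outcome, but it sets the arm size used below. For 50% versus 80%, two-sided alpha 0.05 and power 80%:

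- n = [1.96 × √(2 × 0.65 × 0.35) + 0.842 × √(0.25 + 0.16)]² / 0.30² = 38.5, so 39.
- With the continuity correction: (38.5 / 4) × [1 + √(1 + 4 / (38.5 × 0.30))]² = 44.9, so 45.

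This matches the stated 45 per group. The planned 100 overall gives 50 per arm.

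**Assumed inputs.** The documents give no event rates, SDs or reading interval. The main illustration assumes 50 per arm, events in 25% versus 5% of women, and one 30 mmHg fall lasting 10 of 120 minutes.

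**1. Comparison of 2-hour means.** Each event shifts a woman's mean by 30 × 10 / 120 = 2.5 mmHg. The arms differ by 2.5 × (0.25 − 0.05) = 0.5 mmHg. With an SD of women's means of 5 to 8 mmHg, the standard error is SD × √(2/50) = 1.0 to 1.6 mmHg. The difference is 0.3 to 0.5 standard errors, and power is about 6 to 8%.

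**2. Group-by-time test in repeated-measures ANOVA.** Simulated with readings every 5 minutes, between-woman SD 8 to 10 and within-woman SD 7:

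| Spread of onset between women | 10-min fall | 20-min fall |
|---|---|---|
| All at the same reading | about 64–73% | not needed for the point |
| Over about 25 min | about 24–25% | about 60% |
| Over about 55 min | about 11% | about 25% |

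For 10-minute falls, over a wider range of synchrony and reading noise, power ran from about 8% to 80%.

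**3. Proportion of women with an event.** Summing the two binomial distributions over all tables with a two-sided Fisher p below 0.05 gives about 75% power when true events are known. When the event is read from a noisy lowest value, simulated power was about 47 to 72%.

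**4. The plan's own treatment comparison.** If a share c of episodes is treated and counted, the compared rates are 0.25c and 0.05c. The same Fisher calculation gives:

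| Share counted | Rates compared | Power |
|---|---|---|
| 100% | 0.250 vs 0.050 | 75% |
| 90% | 0.225 vs 0.045 | 68% |
| 75% | 0.1875 vs 0.0375 | 55% |
| 50% | 0.125 vs 0.025 | 30% |

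**5. A second set of rates, 30% versus 10%.** Power is about 6 to 10% on 2-hour means (falls of 10 to 20 minutes) and about 64% on events. It is about 24% on treatment use if half of the episodes are counted. The direction is the same.

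**6. Second study drug.** On the plan's own success rates, 50 × 0.5 + 50 × 0.2 = 35 of 100 women would fail. Study Design and Procedures gives the other study drug to women whose treatment fails within 25 minutes. That falls inside the 2-hour collection period, so later readings in those women reflect both drugs.

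**The case against.** Three stronger readings are tempting, and the documents do not support them.

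- **That treated hypotension vanishes from the comparison.** Ephedrine, fluids, oxygen and positional changes are themselves compared between arms. A treated episode is what those outcomes count. If 90% or more of episodes are treated and counted, that comparison has 68 to 75% power, close to the event test. A large loss needs many uncounted episodes, and the documents do not show that this would happen.
- **That the plan compares a single 2-hour average.** It allows repeated measurements, and a group-by-time test can detect falls that cluster after one bolus. Setting 6 to 8% against 75% would therefore misstate the plan. What remains is that this test compares group means at each time. Its power falls away as onset varies, and the plan does not fix the reading interval on which it depends.
- **That the association phrase requires a causal judgement, perhaps by unblinded staff.** It may be a loose description of timing, or may attach only to positional changes. No adjudication step is described. Blinding is stated only for the observer, and silence about others does not show that attribution would be unblinded. The missing counting rule stands as a gap.

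Two further objections have force. The trial is framed as an efficacy comparison, so this is a secondary matter. Counting every treatment also has a cost. If 10% of women in each arm have unrelated use, the rates become 1 − 0.75 × 0.90 = 0.325 and 1 − 0.95 × 0.90 = 0.145, and power falls from about 75% to 49%.

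**Conclusion.** The concern holds in a limited form. The planned analysis of blood pressure and heart rates compares means and never compares women with an episode. It can miss brief falls with variable onset, and the treatment counts can miss falls that are untreated or not attributed. Treated episodes are partly captured.

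The size of the loss depends on facts the plan does not supply. It is small if falls are tightly synchronised or nearly all are treated and counted. It is large if onset is scattered and about half are counted: about 11% on the group-by-time test (10-minute falls, onset over 55 minutes) and 30% on treatment use, against 47 to 75% for an event comparison. These figures illustrate assumed values and do not predict this trial's results. The change is worth making before the data are seen by arm. It adds a comparison better suited to brief harms, and it prevents a cut-off from being chosen after the results are known.

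**What to change.** In the Statistical Procedures section:

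1. Add per-woman safety outcomes: the lowest post-dose systolic pressure relative to the pre-dose value, the proportion with maternal hypotension, and the proportion with a fetal heart rate event. The sponsor should set the thresholds, and any duration rule, before unblinding.
2. Compare the two proportions by randomised arm with a risk difference and 95% CI. Keep the ANOVA as supporting analysis.
3. Replace the undefined association with one fixed time window from the study dose for counting ephedrine, oxygen, fluid boluses and positional changes. Report treatment use separately from the pressure-defined event, so that unrelated use does not dilute it.
4. Report events before and after any second study drug separately, alongside the comparison over the whole window.
5. State the measurement interval, since both the lowest value and the ANOVA depend on it.

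The cost is a paragraph of protocol wording and a short table, because the underlying data are already to be collected. The downside is that a fixed-window count includes some unrelated uses, with the dilution shown above.
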